19. **PREGNANCY TEST:** Perform only in female subjects of childbearing potential.
 20. **PREGNANCY TEST:** A **serum** pregnancy test should be performed no more than 7 days prior to the first dose of study treatments.
 21. **PREGNANCY TEST:** A **serum or urine** pregnancy test will be performed every 8 weeks during the first 48 weeks of study treatment, then every 12 weeks thereafter, and at the Follow-up Visit.
 22. **MONITORING for NON-CUTANEOUS SECONDARY/RECURRENT MALIGNANCY:** During study treatment, monitor as clinically appropriate which may include a head/neck exam every 3 months and a chest/abdominal CT scan or MRI every 6 months.
 23. **MONITORING for NON-CUTANEOUS SECONDARY/RECURRENT MALIGNANCY:** This assessment is to be part of the physical exam and should include visual inspection of the oral mucosa and lymph node palpation.
 24. **MONITORING for NON-CUTANEOUS SECONDARY/RECURRENT MALIGNANCY:** Following discontinuation of study treatments, monitoring (which may include a chest/abdominal CT scan or MRI) should continue for up to 6 months or until initiation of new anti-cancer therapy.
 25. **DISEASE ASSESSMENTS (Solid Tumor Cohorts only):** See Section 7.5.1 for details on baseline and post-baseline disease assessments for the solid tumor cohorts: ATC, ASI, BTC, GIST, NSGCT/NGGCT and WHO Grade 1-4 Glioma.

26. **DISEASE ASSESSMENTS (Solid Tumor Cohorts only):** Baseline disease assessments must be performed within 28 days prior to enrollment (or within 35 days if MRI is used for disease assessment).
27. **DISEASE ASSESSMENTS (Solid Tumor Cohorts only):** Disease assessments are every 8 weeks during the first 48 weeks of study treatment, then every 12 weeks thereafter unless otherwise noted, and at the Follow-up Visit. Confirmatory scan(s) are to be performed ≥ 28 days after documented CR or PR. If subject discontinues treatment for reasons other than disease progression, disease assessments should continue every 12 weeks until disease progression, initiation of new anti-cancer treatment, subject withdrawal of consent, or death.
28. **HISTOLOGY CONFIRMATION: (ATC and WHO grade 1-4 cohorts only)** A tissue specimen for possible retrospective histology confirmation should be obtained and submitted to a Novartis designated central reference laboratory. Please refer to the SPM for the requirements of the tissue specimen that is required for the histology confirmation.

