38. **MM ONLY:** BM aspirate and BM biopsy samples will be assessed by IHC, flow cytometry, FISH and cytogenetics **within 90 days prior enrollment**.

39. **MM ONLY:** Flow cytometry for plasma cell enumeration and phenotyping will be performed on BM aspirate and BM biopsy samples at Week 8 and then at the time of achieving a CR or best response. **NOTE:** Density gradient is not recommended.
40. **MM ONLY:** SPEP should be performed **within 28 days prior to enrollment**, every 4 weeks for the first 48 weeks of study treatment, then every 12 weeks thereafter, and at the Follow-up Visit.
41. **MM ONLY:** UPEP must be performed using a 24-hr urine sample.
42. **MM ONLY:** If UPEP is positive at Screening (**or within 28 days prior to enrollment**), then a UPEP should be performed every 4 weeks for first 48 weeks of study treatment, then every 12 weeks thereafter, and at the Follow-up Visit.
43. **MM ONLY:** CRP, β 2 microglobulin; immunoglobulins (IgG, IgA and IgM) and serum FLC assay should be performed **within 28 days prior to enrollment**, every 4 weeks for the first 48 weeks of study treatment, then every 12 weeks thereafter, and at the Follow-up Visit.
44. **PK Sampling - Week 4:** Two 2-mL blood samples for PK analysis of trametinib, dabrafenib and its metabolites (hydroxy-dabrafenib and desmethyl-dabrafenib) will be collected at Week 4. **For subjects with a morning clinic visit:** Subjects will be instructed to withhold their morning doses of study treatment prior to the study visit. The first PK blood sample (pre-dose) will be obtained prior to dabrafenib administration (between 8 to 14 hrs after the evening dose of dabrafenib on the previous day). The second PK blood sample (post-dose) will be obtained 1 to 3 hrs following administration of dabrafenib. **For subjects with an afternoon clinic visit:** Subjects will be instructed to take their morning doses of study treatments as usual. The first PK blood sample (pre-dose) will be obtained 4 to 8 hrs following dabrafenib administration. The second PK blood sample (post-dose) will be obtained 1 to 3 hrs following administration of dabrafenib.

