45. **PK Sampling - Week 8, Week 12, and Follow-up Visit:** A single 2 mL blood sample for PK analysis of trametinib, dabrafenib and its metabolites (hydroxy-dabrafenib and desmethyl-dabrafenib) will be collected at Week 8 (pre-dose), Week 12 (pre-dose), and at the Follow-up Visit. Subjects with morning clinic visits are to be instructed to withhold their morning doses of study treatment and PK samples will be collected prior to dabrafenib administration. Subjects with afternoon clinic visits are to be instructed to take their morning doses as usual and PK samples will be collected 4 to 8 hrs following dabrafenib administration. **Samples at the Follow-up Visit are no longer requested for collection as of Protocol Amendment 11.**

[REDACTED]

- 
54. **STUDY TREATMENT:** Subjects must receive their supply of study treatments within 3 days of enrollment.
55. **FOLLOW-UP VISIT:** The Follow-up Visit should take place within 28 days (+7 days) of the last dose of study treatments. If the subject is unable to return to clinic, site staff is encouraged to call subject for assessment of AEs.
56. **FOLLOW-UP VISIT:** All safety and laboratory assessments should be performed unless the assessments were performed within 4 weeks prior to the Follow-up Visit.
57. **FOLLOW-UP VISIT:** If the last cardiac assessment was >12 weeks prior to the Follow-up Visit, an ECHO should be performed.
58. **EXTENDED FOLLOW-UP:** The following evaluations will be performed for all patients in all cohorts.
- a) Dermatologic exam. Exams will be performed every 4 weeks (+/-7 days) for the first 6 months. The skin will be carefully examined and pictures and biopsy will be taken of any new or changed skin lesions.
 - b) If study treatments are permanently discontinued prior to the subject having confirmed disease progression, the subject will continue to have disease assessments every 12 weeks (+/-14 days) until disease progression or initiation of new anti-cancer treatment, or death, whichever comes first.
 - c) Subjects will be followed every 12 weeks (+/-14 days) for survival until the subject dies or withdraws consent or is lost to follow up, or up to a time period as defined in Section 16.3. Survival follow up may be performed via clinic visit, a telephone contact, an email or by mail. The initiation of any new anti-cancer treatment(s) and date of last contact should also be documented.

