Summaries of reasons for censoring DoR by both investigator assessment and independent radiology review will be produced with additional information about censoring due to COVID-19 related protocol deviations. The number and percentage of subjects with each censoring reason (1. PD or death after ≥ 2 consecutive missed visits, 2. New anti-cancer treatment started prior to documented PD, 3. No baseline (or adequate post-baseline) assessments, 4. No progression or death, separated into follow-up ended and follow-up ongoing) will be displayed along with relevant COVID-19 related censoring reasons (study withdrawal due to COVID-19 and missing visits due to COVID-19) derived from protocol deviations data. Further details of these outputs are given in the programming notes to the TFL shells.

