4.2 Extended Loss to Follow-up or Extended Time without an Adequate Assessment

Since missing scheduled disease assessments prior to progression or death increases the uncertainty about when the event actually occurs, PFS and DoR will be censored for subjects who have progression or die after missing two or more scheduled disease assessments. Specifically, if there are two or more scheduled assessments which are missing followed by progression or death, PFS and DoR will be censored at the last adequate assessment prior to progression or death.

For the purpose of this calculation, the last adequate assessment is defined as the last assessment prior to progression or death with response other than NE or missing.

For solid tumor cohorts (ATC, BTC, GIST, NSGCT/NGGCT, ASI, WHO Grade 1 or 2 Glioma and Grade 3 or 4 Glioma) and MM cohort, when the scheduled disease assessment is every 8 weeks (for the first 48 weeks of study treatment), a window of 119 days (16 weeks + 7 day window) will be used to determine whether there was an extended time without adequate assessment. When the scheduled disease assessment is every 12 weeks (after the first 48 weeks of study treatment), a window of 175 days (24 weeks + 7 day window) will be used to determine whether there was an extended time without adequate assessment. Specifically, extended lost-to-follow-up period is defined using different time windows as described in [Table 4-1](#).

Table 4-1 Extended lost-to-follow-up period at different study times

Last adequate assessment	Extended lost-to-follow-up period
<= end of week 44	16 + 1 weeks (119 days)

Last adequate assessment	Extended lost-to-follow-up period
(<=308 days)	
>= beginning of week 45 – <= end of week 54 (>308 days, <=378 days)	20 + 1 weeks (147 days)
>= beginning of week 55 (>378 days)	24 + 1 weeks (175 days)

For the HCL cohort, the scheduled disease assessment is every 4 weeks for the first 48 weeks of study treatment, then at least every 8 weeks for patients tolerating the study drug in the judgement of the treating investigator. Following protocol amendment 11, the interval between assessments beyond the first 48 weeks is increased to at least every 12 weeks. To provide reasonable allowance for missed assessments within the new schedule, the same rules will be used for HCL as for the solid tumor cohorts and MM to determine whether there was an extended time without adequate assessment.

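### For five solid-tumour cohorts, SAP Table 4-1 censors progression after one missed scan when the last adequate scan is week 40 or week 48, although SAP 4.2 requires two misses

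*SAP*

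**What the plan says.** SAP 4.2 gives the rule in words: "PFS and DoR will be censored for subjects who have progression or die after missing two or more scheduled disease assessments". The subject is then censored at the last adequate assessment before the event. The same section gives a window of 119 days while scans are 8-weekly and 175 days once they are 12-weekly.

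Table 4-1 sets the window by the day of the last adequate assessment:

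- up to day 308 (end of week 44): "16 + 1 weeks (119 days";
- after day 308 and up to day 378 (weeks 45 to 54): "20 + 1 weeks (147 days";
- after day 378: 175 days.

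The solid-tumour schedule is in Protocol 7.1, footnote 27: "Disease assessments are every 8 weeks during the first 48 weeks of study treatment, then every 12 weeks thereafter unless otherwise noted". Table 4 of the protocol allows ±3 days at these visits.

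SAP 2.6.1 and 2.6.2 list the censoring reasons to be tabulated. One is "PD or death after ≥ 2 consecutive missed visits".

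SAP 2.6 limits the secondary efficacy analyses to ATC, BTC, ASI, the two glioma cohorts, MM and HCL.

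**The concern.** The table is meant to carry out the two-miss rule. The interval between scans changes at week 48, so the time spanned by one missed scan also changes around that visit. If the row cut-offs do not follow the change, a subject who misses a single scan is treated as one who missed two.

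A progression that the stated rule counts would then be replaced by censoring at the last adequate scan. The reason list has no entry for a single miss, so such a subject would fall under the reason for two or more. In a single-arm trial, dropping events in this way raises the later part of the PFS and DoR curves, including the 24-month estimates that SAP 2.6.1 and 2.6.2 ask for.

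**Working it through.** **Inputs.** Scan weeks 8, 16, 24, 32, 40, 48, 60, 72, 84 and so on (Protocol 7.1, footnote 27); ±3 days per visit (Protocol Table 4); windows and cut-offs from SAP Table 4-1.

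**The plan's own figures.** Window = weeks spanned × 7 + 7: 16 × 7 + 7 = 119; 20 × 7 + 7 = 147; 24 × 7 + 7 = 175. Cut-offs: 44 × 7 = 308; 54 × 7 = 378. All reproduce.

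**Gap after one missed scan.** Gap = (week of the second scheduled scan after the last adequate one − week of the last adequate scan) × 7. The event is censored if the gap exceeds the window. The range adds −6 to +6 days, for ±3 days at each end.

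| Last adequate scan | Missed | Progression found | Gap in days (range) | Table 4-1 window | Result |
|---|---|---|---|---|---|
| Weeks 8 to 32 | next scan | 16 weeks later | 112 (106–118) | 119 | event |
| Week 40 (day 280) | week 48 | week 60 | 140 (134–146) | 119 | censored |
| Week 48 (day 336) | week 60 | week 72 | 168 (162–174) | 147 | censored |
| Week 60 onward | next scan | 24 weeks later | 168 (162–174) | 175 | event |

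Each of the two failing visits fails in all 49 combinations of ±3-day offsets. No other scheduled on-treatment scan fails, and two misses are always censored.

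**Where the slip is.** The span from week 40 to week 60 is 8 + 12 = 20 weeks, which is the 147-day window, but week 40 sits in the 119-day row. The span from week 48 to week 72 is 12 + 12 = 24 weeks, which is the 175-day window, but week 48 sits in the 147-day row. The week-48 row also conflicts with the sentence in SAP 4.2 that gives 175 days for the 12-weekly phase. If the schedule were instead read as weeks 40, 52, 64, single misses would be censored at last adequate scans of week 32 (140 > 119), week 40 (168 > 119) and week 52 (168 > 147), so the finding does not depend on how the switch is read.

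**Re-cut at 252 and 308 days.** Week 40: 140 ≤ 147, event; two misses, (72 − 40) × 7 = 224 > 147, censored. Week 48: 168 ≤ 175, event; two misses, (84 − 48) × 7 = 252 > 175, censored. Across all ±3-day combinations at scheduled scans there are no failures.

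**Size (assumed inputs).** Exponential progression, independent misses at 5%, 10% and 20%, 36 months of follow-up, progression found only at scheduled scans, ±3-day windows. Kaplan-Meier estimates under the current and re-cut tables were compared in simulation.

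| Median PFS | Rise in 24-month PFS, 5% to 20% misses (percentage points) |
|---|---|
| 3 months | about 0.03 to 0.15 |
| 6 months | about 0.3 to 1.2 |
| 12 to 24 months | about 0.6 to 2.2 |

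Over these settings about 0.6–4.5% of progression events are lost. The lost progressions are dated at week 60 or 72, after 12 months, so 12-month PFS is not raised.

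**The case against.** The strongest objection is to carrying the point further than the two rows. Most of it stands.

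- **All solid tumours.** A reader might extend the point to every solid-tumour cohort. SAP 2.6 leaves GIST and NSGCT/NGGCT out of the PFS and DoR analyses.
- **HCL.** SAP 4.2 applies the table to HCL deliberately: "To provide reasonable allowance for missed assessments within the new schedule". That is a stated choice, not a slip.
- **MM.** SAP 4.2 treats MM as 8-weekly. The protocol schedules serum electrophoresis "every 4 weeks for the first 48 weeks of study treatment, then every 12 weeks thereafter, and at the Follow-up Visit", but extramedullary assessment every 8 weeks. Until these are reconciled, the correct MM window cannot be derived.
- **Off treatment.** After stopping without progression, "the subject will continue to have disease assessments every 12 weeks (+/-14 days) until disease progression or initiation of new anti-cancer treatment", while Table 4-1 depends only on study time. A fixed 196-day row looks tempting: one miss spans at most 168 + 28 = 196 days, and progression at a scheduled scan after two misses at least 252 − 28 = 224. But the tolerance for the second missed scan closes at 168 + 14 = 182 days, so a death at days 183–196 follows two misses and would still count as an event.
- **Unscheduled dates.** The clean result for the re-cut table covers only progression at scheduled scans. Counting week w as day 7w + 1, a confirmatory scan 28 days after a week-32 or week-40 response falls on day 253 or 309, one day past the new cut-offs. Deaths or unscheduled progression after two misses could then count up to day 253 + 147 = 400 or 309 + 175 = 484, against 372 and 456 under the current table.
- **Labelling.** The SAP refers to programming notes in the output shells, which are not among the documents, so how the reason is finally printed cannot be verified.

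None of this rescues the week-40 and week-48 rows. A reply that the table governs would leave it contradicting the rule stated in the same section.

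**Conclusion.** Wrong as written, and minor. For ATC, BTC, ASI and the two glioma cohorts, Table 4-1 contradicts the two-miss rule at last adequate scans of week 40 and week 48. This follows from date arithmetic and needs no assumption.

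The size does rest on assumptions, since the documents give no missed-scan rate and no expected PFS by cohort. A reader might take the 0.6 to 2.2 points as applying everywhere. That range belongs to medians of 12 to 24 months; with a 3-month median the shift is negligible. Nor is 12-month PFS inflated. DoR at 24 months is expected to move in the same direction as PFS. Both are descriptive secondary endpoints. ORR, its decision rule and OS do not use this table.

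**What to change.** For ATC, BTC, ASI and the two glioma cohorts, re-cut Table 4-1 by day of last adequate assessment:

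- up to day 252: 119 days;
- after day 252 and up to day 308: 147 days;
- after day 308: 175 days.

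State that where the last adequate scan is off the schedule (such as a confirmatory scan), or the event is a death or an unscheduled progression, the scheduled assessments actually missed are counted instead of applying a day window. Use the same count for subjects followed off treatment without progression, and do not add a fixed 196-day row.

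Leave HCL and MM on the current table. For MM, first reconcile the SAP's 8-weekly description with the protocol's 4-weekly laboratory tests and 8-weekly extramedullary assessment.

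The cost is one table, a short counting rule and the matching programming. No new data are needed.

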4.3 Date Associated with Response

For MM and HCL, investigator assessment of disease is entered in the eCRF on the VISIT form. The date of the VISIT is captured but the date of the response assessment is not captured separately. The date associated with response will be the visit date for the VISIT on which the investigator assessed disease. A disease assessment may occur at an unscheduled visit. The date of the unscheduled visit would be assigned to any response assessed on that date.

For all solid tumor histologies, for each disease assessment after baseline, determine a date associated with the response. For complete response (CR), partial response (PR), and when applicable minor response (MR), assign to the latest date within the disease assessments. For stable disease (SD), Non-CR/Non-PD or Not Evaluable, assign to the earliest date within the disease assessments. For progressive disease (PD), assign to the earliest assessment date associated with the progression.

4.4 Imputation rules

Partial dates may be imputed for ‘slotting’ data to study time periods or for specific analysis purposes as outlined below.

4.4.1 Demography (ADSL)

Dataset	Date	Missing Element	Rule
ADSL	Birth date (BRTHDT)	day, month, and year	No Imputation for completely missing dates
		day and month	Imputed to June 30

4.4.2 Initial diagnosis of primary tumor type under study

Dataset	Date	Missing Element	Rule
Disease Characteristics (ADDC)	Initial Diagnosis Date	day, month, and year	No imputation for completely missing date
		day, month	Impute the missing month and day as January 1
		day	Impute the missing day as 1st of the month.

4.4.3 Adverse events (ADAE)

Imputations in the adverse events dataset are used for slotting events to the appropriate study time periods and for sorting in data listings.

Dataset	Date	Missing Element	Rule
Adverse Events (ADAE)	Start Date	day, month, and year	No Imputation for completely missing dates
		day, month	
 • If study treatment start date is missing (i.e. subject did not start study treatment), then set start date = January 1. • Else if study treatment start date is not missing: 
 ○ If year of start date = year of study treatment start date then 
 • If stop date contains a full date and stop date is earlier than study treatment start date then set start date = January 1. • Else set start date = study treatment start date. ○ Else set start date = January 1.
		day	
 • If study treatment start date is missing (i.e. subject did not start study treatment), then set start date = 1st of month. • Else if study treatment start date is not missing: 
 ○ If month and year of start date = month and year of study treatment start date then 
 • If stop date contains a full date and stop date is earlier than study treatment start date then set start date= 1st of month. • Else set start date = study treatment start date. ○ Else set start date = 1st of month.
	End Date		No imputation for partial end dates will be performed

4.4.4 Surgery and radiotherapy

The following imputation will be used for surgical procedures and start dates of radiotherapy. End dates of radiotherapy will not be imputed.

Dataset	Missing Element	Rule
Surgical Procedures and Radiotherapy (ADPR)	day, month, and year	
 No Imputation for completely missing dates
	day, month	
 If partial date contains a year only set to January 1st.
	day	
 If partial date contains a month and year set to the 1st of the month

4.4.5 Concomitant medication and blood and blood supportive care products

Impute start and end dates for use in derivation of the reference variables, concomitant medication start and end relative to treatment and blood and blood supportive care start and end relative to treatment, but do not permanently store the imputed start and end dates in the analysis datasets. The reference variables will be used to differentiate before, during and after for the concomitant medication or blood or blood supportive care start and end dates.

Dataset	Date	Missing Element	Rule
Concomitant Medication Blood and Blood Supportive Care Products	Start Date	day, month, and year	
 No Imputation for completely missing dates
		day, month	
 If study treatment start date is missing (i.e. subject did not start study treatment), then set start date = January 1. Else if study treatment start date is not missing: 
 If year of start date = year of study treatment start date then 
 If stop date contains a full date and stop date is earlier than study treatment start date then set start date = January 1.

Dataset	Date	Missing Element	Rule
			
 ▪ Else set start date = study treatment start date. ○ Else set start date = January 1.
		day	
 • If study treatment start date is missing (i.e. subject did not start study treatment), then set start date = 1st of month. • Else if study treatment start date is not missing: 
 ○ If month and year of start date = month and year of study treatment start date then 
 ▪ If stop date contains a full date and stop date is earlier than study treatment start date then set start date= 1st of month. ▪ Else set start date = study treatment start date. ○ Else set start date = 1st of month.
	End Date	day, month, and year	
 • No Imputation for completely missing dates
		day, month	
 • If partial end date contains year only, set end date = earliest of December 31 or date of last contact.
		day	
 • If partial end date contains month and year, set end date = earliest of last day of the month or date of last contact.

4.4.6 Time to event (Duration of response and Progression-free survival) and best confirmed overall response

On-therapy or follow-up anti-cancer therapy, including radiotherapy and cancer-related surgery start dates, may be imputed to determine date of first new anti-cancer therapy, in order to define event and censoring dates for progression-free survival and duration of response and inclusion of correct records in derivation of best confirmed overall response.

Dates will only be imputed when a month and year are available but the day is missing. In this case, only the date of first new anti-cancer therapy (not all anti-cancer therapy and radiotherapy start dates) will be stored on appropriate efficacy datasets.

The date of first new anti-cancer therapy is derived as the earliest date of new anti-cancer therapy (e.g. chemotherapy), radiotherapy, or cancer related surgical procedure and will include imputed dates. If the date is an imputed date, then the flag variable is assigned the value of 'D' to indicate that the day portion of the date is imputed (following ADaM convention).

As multiple dates are used to derive the new anti-cancer therapy date ensure that the flag is only set to 'D' if the derived date is imputed. For example, if the date of new radiotherapy is imputed but the date of new systemic anti-cancer therapy is prior to date of new radiotherapy and the new systemic anti-cancer therapy date is not a partial date then the flag should be set to missing as the date used for first new anti-cancer therapy is not an imputed date. The following rules will be used to impute the date when partial start dates are present.

Dataset	Date	Missing Element	Rule
Anti-Cancer Therapy Where applicable: Radiotherapy Surgical Procedures	Start Date	day, month, and year	
 No Imputation for completely missing dates
		day, month	
 No imputation for missing day and month (note the eCRF should only allow for missing day)
		day	
 If partial date falls in the same month as the last dose of study treatment, then assign to earlier of (date of last dose of study treatment+1, last day of month). If partial date falls in the same month as the subject's first occurrence of PD, then assign to earlier of (date of PD+1, last day of month). If both rules above apply, then assign to latest of the 2 dates Otherwise, impute missing day to the first of the month.
	End Date		
 No imputation for partial end dates will be performed

